11.4 ELECTROCARDIOGRAM

Descriptive statistics for ECG parameters (heart rate, RR interval, PR interval, QRS interval, QT interval, and QTc) at baseline and changes from baseline values at each assessment time point (including the end of the double-blind treatment period) will be presented by treatment group. The QTc will be calculated using both the Bazett and Fridericia corrections. Only patients with available baseline and at least 1 postbaseline assessment will be included in the summary.

Electrocardiographic parameter values are considered PCS if they meet or exceed the higher-limit PCS criteria listed in Table 11–3. The number and percentage of patients with PCS postbaseline ECG values will be tabulated by treatment group for the double-blind treatment period. The percentages will be calculated relative to the number of patients with available non-PCS baseline values and at least 1 postbaseline assessment for the double-blind treatment period. The numerator is the total number of patients with available non-PCS baseline values and at least 1 PCS postbaseline value for the double-blind treatment period. A supportive tabular display of patients with PCS postbaseline values will be provided, including the PID number, baseline, all postbaseline (including non-PCS) values, and change from baseline.

In addition, a listing of all AEs that occurred in patients who had postbaseline PCS ECG values will be provided.

Table 11–3. Criteria for Potentially Clinically Significant Electrocardiograms

Parameter	Unit	Higher Limit
QRS interval	msec	≥ 150
PR interval	msec	≥ 250
QTcB	msec	>500
QTcF	msec	> 500

QTcB = QT interval corrected for heart rate using the Bazett formula $(QTcB = QT/(RR)^{1/2})$; QTcF = QT interval corrected for heart rate using the Fridericia formula $(QTcF = QT/(RR)^{1/2})$

A listing of patients with postbaseline clinically significant ECG abnormalities as reported by the central laboratory and the Investigators will be provided.

The number and percentage of patients with an increase > 30 msec but ≤ 60 msec, and with an increase > 60 msec in QTcB or QTcF will be tabulated. A supportive listing of patients with postbaseline QTcB or QTcF increases > 30 msec will be provided, including the PID number, and all QTcB and QTcF values (including changes from baseline). A listing of all AEs for patients with postbaseline QTcB or QTcF increases > 30 msec will also be provided.

A shift table from baseline to the end of double-blind treatment period in the Investigator's overall interpretation of the ECG will be presented by treatment group for the following categories: normal; abnormal, not clinically significant; abnormal, clinically significant.

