Vital sign values will be PCS if they meet both the observed-value criteria and the change from baseline-value criteria. The criteria for PCS vital sign values will be detailed in the Statistical Analysis Plan. The percentages will be calculated relative to the number of patients with baseline values and at least 1 postbaseline assessment. The numerator will be the total number of patients with available baseline values and at least 1 PCS postbaseline value. A supportive listing of patients with PCS postbaseline values will be provided, including the PID number, study center number, and baseline and postbaseline values.

9.7.6.4 *Electrocardiogram*

Descriptive statistics for ECG parameters (ie, ventricular heart rate, RR interval, PR interval, QRS interval, QT interval, and QTc interval) and changes from baseline values at each assessment time point will be presented by treatment group. The QTc interval is calculated using the Bazett and Frederica corrections.

The number and percentage of patients with PCS postbaseline ECG values will be tabulated by treatment group. The criteria for PCS ECG values will be detailed in the Statistical Analysis Plan. The percentages will be calculated relative to the number of patients with available non-PCS baseline values and at least 1 postbaseline assessment. The numerator will be the total number of patients with available non-PCS baseline values and at least 1 PCS postbaseline value. A supportive listing of patients with PCS postbaseline values will be provided, including the PID number, study center number, and baseline and postbaseline values.

A listing of patients with postbaseline clinically significant ECG abnormalities, as reported by the Investigator or by the central cardiologist, will also be provided.

The number and percentage of patients with an increase > 30 msec but ≤ 60 msec, and with an increase > 60 msec in QTcF will be tabulated. A supportive listing of patients with postbaseline QTcF increases > 30 msec will be provided, including the PID number, study center, and all QTcF values (including changes from baseline). A listing of all AEs for patients with postbaseline QTcF increases > 30 msec will also be provided.

9.7.6.5 *Other Safety Parameters*

9.7.6.5.1 *Columbia-Suicide Severity Rating Scale*

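### SAP 11.4 extends the QTc-increase categories and both listings from QTcF to QTcB or QTcF without declaring it, and the Table 11-3 footnote prints the wrong QTcF exponent

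*SAP*

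**What the plan says.** Protocol 9.7.6.4 (Electrocardiogram) uses both corrections for descriptive statistics: "The QTc interval is calculated using the Bazett and Frederica corrections". For the increase categories it uses one, counting patients "with an increase > 60 msec in QTcF will be tabulated", with the band above 30 and up to 60 msec in the same sentence. The patient listing follows the same rule: "A supportive listing of patients with postbaseline QTcF increases > 30 msec will be provided". The listing of adverse events in those patients is also triggered by QTcF. What the section leaves to the SAP is the set of potentially clinically significant (PCS) limits: "The criteria for PCS ECG values will be detailed in the Statistical Analysis Plan". The increase categories are not left open.

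SAP 11.4 counts patients "with an increase > 60 msec in QTcB or QTcF will be tabulated" and uses the same pair of corrections as the trigger for the patient listing and the adverse-event listing. The patient listing is to show both corrections, "including the PID number, and all QTcB and QTcF values (including changes from baseline". SAP 18.0, the section for departures from the protocol, reports none.

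The footnote to SAP Table 11-3 describes QTcF as "using the Fridericia formula $(QTcF = QT/(RR)^{1/2" (the quotation stops at the exponent, one half). It gives QTcB the same exponent. The SAP abbreviation list (3.0) and the protocol abbreviation list (4.0) both give QTcF the exponent 1/3.

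**The concern.** There are two separate defects. First, the SAP changes the measure behind a prespecified safety tabulation and two listings, in a place the protocol did not delegate, and its own change section says nothing changed. The wording is also incomplete. If it means one count of patients who exceed the threshold on either correction, the result differs from the protocol's. It also leaves open which band applies when the two corrections fall in different bands.

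Second, a formula printed directly under the table of QTcF limits is wrong by the documents' own definitions.

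What is at stake is how an outlier table reads by arm. Bazett values rise with heart rate even when the Fridericia value is constant. The protocol introduction describes the test drug as more potent in vitro on norepinephrine than on serotonin reuptake, so a difference in heart rate between arms is conceivable. A combined count could then show an arm difference that a QTcF count would not.

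**Working it through.** There is no plan figure to reproduce here. The check is a comparison of texts followed by arithmetic from the documents' formulas.

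**Texts side by side**

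| Item | Protocol 9.7.6.4 | SAP 11.4 |
|---|---|---|
| Descriptive QTc | Bazett and Fridericia | Bazett and Fridericia |
| Increase categories | QTcF | QTcB or QTcF |
| Patient listing trigger | QTcF | QTcB or QTcF |
| Adverse-event listing trigger | QTcF | QTcB or QTcF |
| Values shown in listing | QTcF | QTcB and QTcF |

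**Relation between the corrections.** The abbreviation lists give QTcB = QT/RR^(1/2) and QTcF = QT/RR^(1/3). Dividing, QTcB = QTcF × RR^(-1/6). With RR = 60/HR this is QTcB = QTcF × (HR/60)^(1/6).

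**Heart rate alone.** Assume QTcF is fixed at 400 msec (an assumption, not a document figure) and start from 75 bpm, where QTcB = 400 × (75/60)^(1/6) = 415.2.

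- 95 bpm: 400 × (95/60)^(1/6) = 431.8, a rise of 16.7 msec (before rounding).
- 115 bpm: 445.8, a rise of 30.7 msec.
- Crossing 30 msec needs about +39 bpm. Over QTcF of 380 to 420 msec and starting rates of 60 to 90 bpm, the range is about +31 to +48 bpm.
- Crossing 60 msec needs about +94 bpm, with a range of about +74 to +116 bpm.

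**Heart rate plus some real QTcF change** (baseline QTcF 400 msec, 75 bpm)

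- QTcF +20 msec and 95 bpm: 420 × (95/60)^(1/6) = 453.4, and 453.4 − 415.2 is about 38 msec. This patient is below 30 msec by the protocol rule and above it on QTcB.
- QTcF +40 msec and 105 bpm: 440 × (105/60)^(1/6) = 483.0, a rise of about 68 msec. The patient is in the middle band on QTcF and in the top band on QTcB.

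**How far a combined count could move.** This is an illustration only; every input is an assumption. Take no QTcF effect, baseline QTcF 400 msec, baseline heart rate 80 bpm (SD 10) and normally distributed changes.

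| SD of QTcF change, SD of HR change | Above 30 msec, QTcF | Either, no HR shift | Either, +10 bpm |
|---|---|---|---|
| 15 msec, 10 bpm | 2.3% | 5.3% | 11.3% |
| 10 msec, 8 bpm | 0.14% | 0.9% | 4.1% |

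In the first row, the share above 60 msec on either correction is 0.05% with no shift and 0.2% at +10 bpm, which is 0.3 of a patient in an arm of 160.

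**Footnote.** If 1/2 were used for both corrections, QTcF would equal QTcB on every record.

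**The case against.** The strongest reply is that the SAP sentence does not prescribe a combined count. Table 11-3 has separate rows for QTcB and QTcF, the section says both are calculated, and the table shells are in a separate document. Separate tabulation is at least as natural a reading, and under it the protocol's QTcF counts survive. This stands. What remains is that the SAP does not say which is meant, that both listings are triggered by QTcB on either reading, and that the addition is undeclared.

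A reader might infer that the SAP counts a heart-rate rise as QTc prolongation, or that the QTcF result is lost. The documents support neither. Rate alone needs a large rise to reach 30 msec. The listing prints every QTcF value and its change, so the protocol's counts can be rebuilt. SAP 11.4 also summarizes heart rate and RR by arm, so a rate-driven pattern would be visible.

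A reader might also take the +15 bpm pulse criterion in SAP Table 11-2 as a sign that the plan expects such shifts. That rule also requires an observed pulse of at least 130 bpm, and no section gives an expected heart-rate effect.

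Finally, the footnote does not show that QTcF will be miscalculated. It names Fridericia, two other places give 1/3, and an error in reading the PDF superscript cannot be excluded.

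**Conclusion.** The point holds as a minor correction. The departure from Protocol 9.7.6.4 is clear from the text, and SAP 18.0 is wrong to report no changes on this item. The footnote, as it reads, contradicts the SAP's own abbreviation list and the protocol.

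The practical effect depends on an unstated choice. With separate rows, the QTcF table is intact and only the listings widen. With a combined count, the number above 30 msec can only equal or exceed the QTcF count, and it grows with heart rate, mainly through borderline patients. The category above 60 msec would barely move. The actual size in this trial cannot be computed, because the documents give neither an expected heart-rate change nor the variability of QTc; the percentages above show the range under assumed values. These are descriptive safety summaries, and the primary analysis, error control and sample size are untouched.

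**What to change.** - In SAP 11.4, tabulate both increase categories on QTcF, as the protocol states.
- If QTcB is kept, show it as a separate supportive row, not merged into one count of patients exceeding on either correction.
- In the patient and adverse-event listings, identify which correction triggered each patient's entry.
- Declare any retained QTcB addition in SAP 18.0.
- Correct the Table 11-3 footnote to QTcF = QT/(RR)^(1/3), and confirm that the programmed derivation uses that exponent.

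The cost is SAP wording, one table shell and a flag in two listings. No extra data are needed. Only a combined screening count is given up, and the separate QTcB row keeps the Bazett information.

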11.5 OTHER SAFETY PARAMETERS

Other safety parameters include Columbia-Suicide Severity Rating Scale (C-SSRS) and growth.

11.5.1 Columbia-Suicide Severity Rating Scale

For the C-SSRS, the number and percentage of patients with any suicidal ideation or suicidal behavior at Baseline (lifetime history), and during the double-blind treatment period and during double-blind down-taper period will be summarized by treatment group for the Safety population. The distribution of responses for the most severe suicidal ideation and the most severe suicidal behavior will also be summarized by treatment group, separately for the lifetime history, the double-blind treatment period, and the double-blind down-taper period. Supportive listings will be provided and will include the PID number, treatment group, visit number, lifetime history, and postbaseline values for each patient. Intensity of ideation, suicidal behavior type, and lethality of suicidal behavior will also be included in these listings. A listing of all AEs occurring in patients who have suicidal ideation or suicidal behavior will also be provided.

11.5.2 Growth Evaluation

Weight and height will be presented as standardized z-scores adjusted for gender and age, using the LMS method (Cole T.J., 1990).

To assess the impact of treatment on growth, the change from baseline to Week 8 in the age-and-gender-adjusted height and weight will be analyzed using an ANOVA model with treatment as factor. A non-parametric (Wilcoxon) test will also be performed.

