9.5.2.10 Vital Signs

Vital sign measurements, seated radial pulse rate, seated systolic and diastolic BP, and body weight, will be documented at every visit. Pulse and BP readings will be taken twice after the patient has been sitting for at least 5 minutes. The second measurement will be entered in the eCRF. A BP cuff of appropriate size for the patient should be used. The same arm and BP cuff should be used for all BP and radial pulse measurements throughout the study.

BP may be measured manually or by machine, but the same method of measurement should be used for a patient throughout the study. Radial pulse rate should be measured manually. All BP and radial pulse measurements will be recorded in the patient's source documents.

Patients should be instructed not to wear clothing with tight sleeves when they come to have their BP measured. Additionally, they should be kept as calm and undisturbed as possible while BP and pulse measurements are taken (ie, there should be no talking while the BP is being measured).

Height will be measured as accurately as possible using a stadiometer while the patient is standing with no shoes on and recorded at Visit 1 (Screening) and Visit 8/ET. Patients should wear their usual indoor clothing, but take off their jacket and shoes during weight measurements. For each patient, body weight and height should be determined using the same equipment during the study after confirming proper calibration.

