For the C-SSRS, the number and percentage of patients with suicidal ideation or suicidal behavior as recorded on the C-SSRS scale will be presented by treatment group. The distribution of responses for most severe suicidal ideation and suicidal behavior during the lifetime history, the double-blind treatment period and the down-taper period will also be presented by treatment group for the Safety Population. Supportive listings will be provided and will include the PID number, treatment group, visit number, lifetime history, and postbaseline values for each patient. Intensity of ideation, suicidal behavior type, and lethality of suicidal behavior will also be included in these listings.

9.7.6.5.2 *Growth Evaluation*

Weight and height will be presented as standardized z-scores adjusted for gender and age, using the lambda-mu-sigma method ([Cole TJ 1990](#)). To assess the impact of treatment on growth, the change from baseline in the age and gender adjusted height will be analyzed using an analysis of variance model with treatment as factor. A non-parametric (Wilcoxon) test will also be performed.

9.7.6.6 *Investigational Product Plasma Concentration Parameters*

Plasma samples will be analyzed for the concentrations of levomilnacipran using validated bioanalytical methods. Population PK parameters will be estimated using nonlinear mixed-effects modeling methods. The study will be prospectively powered to target a 95% confidence interval within 60% and 140% of the geometric mean estimates of clearance and volume of distribution for levomilnacipran ER, with at least 80% power.

9.7.7 *Health Economics and Outcomes Research Analyses*

Not applicable.

9.7.8 *Interim Analysis*

The interim analysis was conducted to identify early signs of futility after 62% of randomized patients had either completed or discontinued the study. The futility assessment of the primary efficacy parameter (CDRS-R total score) on ITT population was based on the conditional power as described in [Lan et al. 1999](#). In calculating the conditional power, it was assumed that the future patients to be enrolled into the Study will have similar efficacy as those of the existing patients of the same treatment group. The non-binding futility criteria was set when the conditional power for detecting a statistically significant treatment difference between the levomilnacipran treatment group

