11.3 VITAL SIGNS

Descriptive statistics for vital signs (sitting radial pulse rate, sitting systolic and diastolic blood pressure, body weight and height) and changes from baseline values at each visit, and at the end of double-blind treatment period, and at the end of double-blind downtaper period will be presented by treatment group. Only patients with available baseline and at least 1 postbaseline assessment will be included in the summary. Vital sign values will be considered PCS if they meet both the observed-value criteria and the change-from-baseline criteria listed in Table 11–2. The number and percentage of patients with PCS postbaseline values will be tabulated by treatment group separately for the double-blind treatment period and the double-blind down-taper period. The percentages will be calculated relative to the number of patients with available baseline and at least 1 postbaseline assessment. The numerator will be the total number of patients with available baseline values and at least 1 PCS postbaseline value. A supportive listing of patients with PCS postbaseline values will be provided, including the PID number, and baseline and all postbaseline (including non-PCS) values.

In addition, a listing of all AEs that occurred in patients who had PCS postbaseline vital sign values will be provided.

	Table 11–2.	Criteria for	Potentially	Clinically	Significant	Vital Signs
--	--------------------	--------------	-------------	------------	-------------	-------------

		Criteria ^a			
Parameter	Flag	Observed Value	Change From Baseline		
Sitting systolic blood	High	≥ 140	Increase of ≥ 20		
pressure, mm Hg	Low	≤ 80	Decrease of ≥ 20		
Sitting diastolic blood	High	≥ 100	Increase of ≥ 15		
pressure, mm Hg	Low	≤ 50	Decrease of ≥ 15		
0:44:	High	≥ 130	Increase of ≥ 15		
Sitting pulse rate, bpm	Low	≤ 45	Decrease of ≥ 15		
Waisht Isa	High	_	Increase of ≥ 7%		
Weight, kg	Low	_	Decrease of ≥ 7%		

a A postbaseline value is considered potentially clinically significant if it meets both the observed-value and the change-from-baseline criteria.

bpm = beats per minute.

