16.1 VISIT TIME WINDOWS

Table 16–1 and Table 16–2 present the visits assigned for efficacy and safety analyses and the corresponding range of treatment days (window) during which an actual visit may occur.

Table 16–1. Visit Time Windows for Double-Blind Treatment Period

Derived Visit	Scheduled Visit Daya	Window
Baseline	Week 0 (Day 1)	Days ≤ 1
Week 1	End of Week 1 (Day 8)	Days [2, 11]
Week 2	End of Week 2 (Day 15)	Days [12, 18]
Week 3	End of Week 3 (Day 22)	Days [19, 25]
Week 4	End of Week 4 (Day 29)	Days [26, 35]
Week 6	End of Week 6 (Day 43)	Days [36, 49]
Week 8	End of Week 8 (Day 57)	Days ≥ 50 days and within double-blind treatment period
End of double-blind treatment period ^b	Final or Termination Visit	during the double-blind treatment period

a Relative to the date of the first dose of double-blind investigational product. Day 1 = the date of the first dose of double-blind investigational product. There is no Day 0 or Week 0.

Table 16–2. Visit Time Windows for the Double-Blind Down-Taper period

Derived Visit	Scheduled Visit	Window
Week 9	End of Week 9	Within the double-blind down-taper period (from 1 day after the end of double-blind treatment period to the end of the double-blind down-taper period)
End of double-blind down-taper period ^a	Final of termination visit during the double-blind down-taper period.	

a Presented in analysis tables for safety parameters collected during the double-blind-down-taper period. If any assessments are repeated at the end-of-double-blind-down-taper-period visit, the algorithm in Section 16.4 will be used to determine which values are used in the analysis.

b Presented in analysis tables for safety parameters, including but not limited to electrocardiograms, clinical laboratory values, and vital signs, and C-SSRS. If repeat assessments occur at the end of double-blind treatment period visit, the algorithm in Section 16.4 will be used to determine which values are used in the analysis.

If the visit date is on or after the date of the first dose of double-blind investigational product, the study day is calculated by visit date – date of the first dose of double-blind investigational product +1. If the visit date is before the date of the first dose of double-blind investigational product, the study day is calculated by visit date – date of the first dose of double-blind investigational product. Therefore, a negative day indicates a day before the start of the double-blind investigational product.

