16.4 REPEATED OR UNSCHEDULED ASSESSMENTS OF SAFETY PARAMETERS

If a patient has repeated assessments before the date of first dose of double-blind treatment period the results from the final nonmissing assessment made before the date of the first dose of double-blind investigational product will be used as baseline. If end-of-double-blind-treatment period assessments are repeated or if unscheduled visits occur, the last nonmissing postbaseline assessment during the double-blind treatment period will be used as the end-of-double-blind-treatment-period assessment for generating summary statistics. Likewise, if end of double-blind down-taper period assessments are repeated or if unscheduled visits occur, the last non-missing assessment during the double-blind down-taper period will be used as the end-of-double-blind-down-taper-period assessment for generating summary statistics. However, all postbaseline assessments will be used to determine PCS values for laboratory parameters, vital signs and ECG parameters, and to determine most severe suicidal ideation and most severe suicidal behavior from C-SSRS. All assessments will be presented in the data listings.

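### The growth test uses only Week 8 values (Day 50 or later), so earlier weights and early-termination heights and weights do not enter it

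*SAP*

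**What the plan says.** Protocol 9.7.6.5.2 (Growth Evaluation) plans that "the change from baseline in the age and gender adjusted height will be analyzed using an analysis of variance model with treatment as factor". It names height only and gives no time point.

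SAP 11.5.2 keeps the treatment-only model but adds weight and a time point: "the change from baseline to Week 8 in the age-and-gender-adjusted height and weight will be analyzed using an ANOVA model with treatment as factor". A Wilcoxon test is to accompany it. SAP 18.0 reports no changes to the protocol's analyses.

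SAP 16.1 says that its window tables "present the visits assigned for efficacy and safety analyses". In Table 16-1 the Week 8 window is "Days ≥ 50 days and within double-blind treatment period". The same table has a separate derived visit for the end of the double-blind treatment period. Its footnote reads: "Presented in analysis tables for safety parameters, including but not limited to electrocardiograms, clinical laboratory values, and vital signs, and C-SSRS". SAP 16.4 gives the rule for that visit: "the last nonmissing postbaseline assessment during the double-blind treatment period will be used as the end-of-double-blind-treatment-period assessment".

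Protocol 9.5.2.10 has weight taken at every visit, while height is "recorded at Visit 1 (Screening) and Visit 8/ET". The schedule of evaluations requires the Visit 8 assessments of all randomized patients, including those who discontinue before Week 8.

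**The concern.** A child who stops on, say, Day 20 and attends the early-termination visit has a post-baseline height and several weights. Table 16-1 assigns the Day 20 values to Week 3, so none of them reaches a test fixed at Week 8. The carry-forward rule in SAP 16.2 is for efficacy variables and does not bring them back.

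For weight, the test also ignores the repeated measurements of every patient, although these carry information about what a missing Week 8 value would have been. The stated rule is therefore less precise than the collected data allow, and more exposed to selective dropout. Growth is a named safety parameter in a required pediatric study, and the only safety parameter given an inferential comparison.

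**Working it through.** **Inputs.** From SAP 14.0: 160 patients per arm (480 in total), 17% dropout, CDRS-R difference 4, SD 11.1, correlation 0.7, power 85%. From SAP Table 16-1: Week 8 starts at Day 50. No figure is given for the growth test.

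**The plan's own figure.**
- Week 8 observed values only: n = 160 × 0.83 = 132.8 per arm. Power = Φ(4/(11.1 × √(2/132.8)) − 1.96) = 83.6%.
- No dropout, n = 160: 89.7%.
- Repeated-measures information formula (compound symmetry, correlation 0.7, six visits, monotone dropout): 86.6% to 87.5% depending on when patients leave, and 86.9% with linear dropout from Week 0.

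The stated 85% lies between the Week-8-only and repeated-measures values, so the planning figures are usable. The contrast also shows that, for a variable with that correlation, a repeated-measures model recovers part of what dropout costs. It says nothing about the correlation of weight z-scores.

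**Patients without a Week 8 growth value.** Excluded per arm = 160 × 0.17 × s, where s is the share of dropout before Day 50. SE ratio = √(160/kept). The difference detectable with 80% power, in SD units of z-score change, is (1.960 + 0.842) × √(2/kept).

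| s (assumed) | excluded per arm | excluded in total | kept per arm | SE ratio | detectable difference |
|---|---|---|---|---|---|
| 1 (ceiling) | 27.2 | 81.6 | 132.8 | 1.098 | 0.344 |
| 49/56 = 0.875 (uniform over Days 1-56) | 23.8 | 71.4 | 136.2 | 1.084 | 0.339 |
| 0.5 | 13.6 | 40.8 | 146.4 | 1.045 | 0.327 |
| no exclusion | 0 | 0 | 160 | 1.000 | 0.313 |

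**Bias.** Suppose the arm difference among excluded patients differs from that among retained patients by d. The estimate is then off by 0.17d at the ceiling, or 23.8/160 = 0.15d with uniform dropout. Neither document gives a value or a sign for d.

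**Baseline covariate.** With equal variances at the two times and correlation ρ, the ANCOVA variance relative to a plain change score is σ²(1 − ρ²)/(2σ²(1 − ρ)) = (1 + ρ)/2. This is 0.995 at ρ = 0.99 and 0.975 at ρ = 0.95 (assumed correlations), a saving of 0.5% to 2.5% of variance.

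**Moving height to the end-of-period value.** As a rough illustration, assume that an effect accrues linearly, that dropout is even over the 8 weeks, that variances are equal and that all early leavers supply a height. Leavers then show half the effect on average, so the pooled effect is 0.83 + 0.17 × 0.5 = 0.915 of the 8-week effect. Multiplied by the precision gain of 1.098, the signal-to-noise ratio is 1.00. Height gains nothing in detectability, and its estimate is diluted.

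**The case against.** **The early values are still reported.** SAP 11.3 summarises "body weight and height) and changes from baseline values at each visit, and at the end of double-blind treatment period", and by SAP 16.4 that last value includes early-termination measurements. Weight changes of 7% or more are flagged using all post-baseline assessments. Adverse events leading to discontinuation are tabulated and listed. This stands: a reader might infer that the plan discards these data from the safety analysis, and it does not. The answer is partial, because the 11.3 summaries name weight and height rather than z-scores, and height has no criterion for clinical significance.

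**It is not a completers-only analysis.** That label is tempting but wrong. Protocol 9.7.2 defines completers by 8 weeks of treatment, so a patient terminating on Days 50-56 is not a completer yet falls in the Week 8 window. Under SAP 11.0, the double-blind period of a patient who takes no taper product runs to the last assessment if that is later than the last dose, so a Visit 9 weight can count too.

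**The SAP does not contradict the protocol.** The protocol left the time point open and specified the same treatment-only model. The SAP narrows an open definition and extends the test to weight. The absent baseline term is not a SAP departure and has no effect on who is included.

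**A fixed Week 8 comparison is defensible.** For height this stands, because the end-of-period value mixes shorter exposures. For weight it does not settle the matter: a repeated-measures model keeps the Week 8 time point and still uses the earlier values.

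**Week 8 might mean the nominal Visit 8/ET.** Table 16-1 covers safety analyses and defines the visit by day, so the text does not support that reading.

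**The test is supplementary.** It has no stated hypothesis, alpha or power, and the protocol synopsis calls the safety analyses descriptive. No primary or secondary conclusion depends on it. This limits the importance of the point.

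**Conclusion.** The concern holds in a limited form. As written, the growth test uses only values from Day 50 on and leaves out earlier weights and early-termination values. The loss is at most about 27 per arm (82 in total), or about 24 per arm (71 in total) with uniform dropout. The standard error is up to 8-10% larger than with a value for everyone.

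These figures assume that the 17% planning rate applies equally to all arms and to the Safety Population. They are ceilings on what can be recovered. Protocol 9.3.3 provides for patients who are lost to follow-up or do not return, and a model at Week 8 recovers information from early leavers only through correlation.

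A reader might go further and infer that the test is biased towards finding no growth effect, on the view that early leavers are those with appetite or weight problems. The documents do not link stopping to growth effects, so the direction of any bias is unknown.

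For weight the remedy is a clear improvement. For height it is a small gain in precision plus a supportive display.

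**What to change.** In SAP 11.5.2:

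- **Weight z-score:** analyse change from baseline with a mixed model for repeated measures on all post-baseline visits. Terms: treatment, visit, treatment-by-visit, baseline z-score and baseline-by-visit. Report the treatment differences at Week 8. The model relies on missingness at random, a weaker assumption than an analysis of Week 8 values alone needs.
- **Height z-score:** keep the Week 8 analysis and add the baseline z-score as covariate. Report the change to the end-of-double-blind-treatment value, already defined in Table 16-1 and SAP 16.4, as a supportive analysis. Note beside it that early values reflect shorter exposure.

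In SAP 18.0, record the Week 8 time point, the addition of weight to the test, and these model changes.

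The cost is SAP wording, one new model call for weight, one added covariate and one supportive table for height. No new data are needed.
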